Study Design	The study is a multi-site study designed to enroll subjects to obtain temperature readings with the welloStationX and a reference thermometer. The data collected will be analyzed to determine clinical bias with stated uncertainty and repeatability of the welloStationX.
Study Procedures	All subjects will have their temperature taken 3 times with the WelloStation, a non-contact infrared thermometer. Another single temperature reading will be taken with a Welch Allyn oral thermometer.
Primary Endpoints	
 • Calculation of clinical bias with stated uncertainty • Calculation of clinical repeatability • Calculation of limit of agreement
Number of Patients	A minimum of 105 subjects.
Number of Sites	Three test sites plus individual home locations.

welloStationX Determination of Clinical Accuracy

Protocol Number: 3939002

PROTOCOL APPROVALS

Project Manager

Date

[name]
Wello, Inc.

Date

INVESTIGATOR APPROVAL

I have read and familiarized myself with this protocol and I agree to conduct the study as described.

Principal Investigator

Date

Wello, INC. REPRESENTATIVES

STUDY SPONSOR

The Clinical Study is sponsored by Wello, Inc. Overall responsibility for the study will be held by and questions regarding clinical and scientific conduct of the study should be addressed to:

[name]
Wello, Inc.
[name]
[name]
[name]
Office [contact]

TEST SITES

1. Wello Inc. Office
[name]
[name]
2. Agape Clinic
[name], Director of Services
[name]
[name]
3. Community Council
[name], EVP
[name]
[name]
4. Individual Homes located in Dallas, Ennis, Frisco and Plano, Texas

STUDY MONITORS

1. [name] – Community Council, September 28; Agape Clinic, October 3rd and October 4th
2. [name] – Agape October 5 and October 16th
3. [name] – Wello Offices and various residences

INSTITUTIONAL REVIEW BOARD (IRB)

IntegReview IRB
[name]
[name]
[contact]
Email: [contact]

LIST OF ABBREVIATIONS

C	Celcius
F	Farenheit
IRB	Institutional Review Board
ISO	International Standard

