4.2 Primary Outcome Analysis

As per ISO 80601-2-56, these measures will be recorded and analyzed as follows:

1. *Clinical Accuracy* will be evaluated by comparing the first recorded measurement using the welloStationX with the single measurement recorded by the Welch Allyn SureTemp oral thermometer.

Results will be presented through:

- (i) Descriptive presentation of means and standard deviations
- (ii) Evaluation of agreement calculated as the clinical bias (mean bias (\pm SD))
- (iii) Limits of Agreement (LOA) calculations
- (iv) Band-Altman plot created using mean bias and standard deviation data
- (v) XY Plot and Correlation Coefficient calculation

2. Repeatability will be calculated using the pooled standard deviations formula.

All analyses will be performed and presented by febrile status (febrile and afebrile) and by device (test device compared with reference device), as applicable.

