The study was a non-randomized, non-blinded single arm design with the subject as his or her own control to evaluate the clinical accuracy of the welloStationX thermometer with respect to that of the standardized Welch Allyn SureTemp oral thermometer in the screening of individuals with fever.

4. Subject Sample

Subjects were 110 males and females aged 5 years of age and older: 33 subjects (30%) were febrile, with fever defined as a core temperature of 99.5°F (37.5°C) or higher; and 77 subjects were afebrile.

Subjects were recruited from amongst non-profit clinical sites and through social media posts for subjects to come to a test site or to be evaluated in his or her own home in the widespread Dallas/Fort Worth area.

Afebrile subjects were compensated with a \$10 gift card and febrile subjects were compensated \$25, the additional amount intended to assist the febrile subject to recovery.

5. Study Procedures

Each subject's temperature was measured three separate times sequentially using the study device, the WelloStationX® (*DUT*) and one time using a new off-the-shelf calibrated Welch Allyn SureTemp oral thermometer with disposable probe covers (the reference thermometer). Each measurement was recorded by a trained technician by following the instructions for use contained in the respective device labeling.

Subject age, gender and race were recorded for each subject, and potential adverse event observation was conducted.

A subject or the subject's guardian was immediately informed if a febrile temperature measurement (99.5°F (37.5°C) or higher) was recorded using the Welch Allyn SureTemp oral thermometer. The subject or guardian will be advised to consider seeking medical attention.

RESULTS

6. Sample Demographics

The sample demographics of gender, age and race are shown below in Tables 1 through 3, respectively, for febrile and afebrile subjects and for subjects overall.

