7.3 Limits of Agreement and Bland Altman Plots

The limits of agreement ($1.96 \times 1\text{SD}$) were calculated (+0.86, -0.80). From this and the mean bias and standard deviation values, a Bland Altman plot of agreement between the test thermometer (welloStationX) and the reference thermometer (SureTemp) in febrile and afebrile subjects was constructed and is shown in Figure 2 below.

Band Altman Plot for Febrile and Afebrile Subjects (n=110)

[figure not shown]

Figure 2: Bland Altman Plot of Agreement Between Study Thermometer (welloStationX) and Reference thermometer (SureTemp) in Febrile and Afebrile Subjects

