7.4 XY Plot and Correlation Coefficient

To further demonstrate the closeness of the relationship between the welloStationX (DUT) and the SureTemp (reference) readings, an XY plot of the two sets of readings was created and is shown in Figure 3 below.

[figure not shown]

Figure 3: XY Plot of welloStationX versus SureTemp for all subjects

$R^2 = 0.80$, indicating a strong linear relationship

8. Clinical Repeatability

Clinical Repeatability was calculated using the pooled standard deviations of the triplicate measurements recorded by the welloStationX.

Table 5 below shows clinical repeatability by febrile status.

Table 5: Clinical repeatability of the welloStationX by febrile status.

Febrile (n=33)	Afebrile (n=77)	All (n=110)
0.13	0.09	0.06

9. Safety Evaluation

There were no observed or reported adverse events for any subject in the study.

DISCUSSION

The results of this clinical study are interpreted both with respect to the study dataset alone and compared to the research data published in the following whitepaper:

Clinical validation of the CAREGIVER® non-contact thermometer model PRO-TF200/PRO-TF300 in febrile and afebrile patients of all ages

Naja E. [name], Alice Huang & Gary O'Hara MSE

November 2013 Copyright ©2013 Thermomedics®, Inc.

This comparison was selected for the following reasons:

1. The reported study clinical data was that which was submitted to the FDA in support of market clearance for the Caregiver Professional Clinical Thermometer (K131771) which is the predicate device in the current submission for K180298.
2. In the reported study, the reference thermometer used was the Welch Allyn SureTemp oral thermometer, the same reference thermometer used in the welloStationX clinical precision study.

There were no notable differences in gender, age or ethnicity by febrile status and age distributions across the spectrum was well represented. Therefore, the subject population was across febrile status was homogenous and the sample overall representative of the intended patient population.

The limits of agreement for the welloStationX are (+0.86, -0.80) which is better than that for the Caregiver study whose limits of agreement was (+0.82, -1.21).

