From the Bland Altman Plot, it is found that only four data points lie just outside the limits of agreement (such that 96.4% of all data points lie within the limits of agreement) which indicates there is a strong agreement between the performance of the welloStationX and the SureTemp and is fewer than the six outliers found in the Caregiver study, most of which also lay further away from the limits of agreement than the four outliers in the welloStationX study.

The limits of agreement did not exceed 0.86 (absolute value) and clinical bias did not exceed 0.03°F for the study population overall. These strong indicators of the close agreement between the performance of the welloStationX and the SureTemp are also superior to those attained in the Caregiver study, where the limits of agreement did not exceed 1.21 (absolute value) and clinical bias did not exceed 0.20 °F for subjects overall.

The highest bias attained was 0.25°F for subjects in the welloStationX febrile subject group, which is still notably lower than the greatest bias attained in the Caregiver study of 0.32°F for subjects in the afebrile group.

The XY Chart further demonstrates the close agreement between the performance of the welloStationX and the SureTemp. The correlation coefficient of 0.80 supports this strong linear relationship.

The notably low clinical repeatability of 0.062 for subjects overall indicates that the absolute difference in repeat measurements taken with the welloStationX is very low and therefore precision across repeated temperature readings is very strong and highly repeatable. Clinical repeatability was comparably high for both the febrile and afebrile subject groups in the welloStationX study, at 0.13 and 0.09, respectively. Each of these clinical repeatability values for the welloStationX thermometer is notably lower than those attained for the Caregiver (0.17 for subjects overall; 0.21 for the febrile subject group and 0.15 for the afebrile subject group).

CONCLUSION

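### Limits of agreement and R² are given only for all 110 subjects although the protocol calls for results by febrile status; the pooled 0.03°F bias averages +0.25 and −0.06

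*SAP*

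**What the plan says.** The Protocol synopsis lists "Calculation of limit of agreement" among the primary endpoints. Protocol 4.2 includes limits of agreement and the correlation coefficient in the primary accuracy analysis and adds: "All analyses will be performed and presented by febrile status (febrile and afebrile) and by device (test device compared with reference device), as applicable".

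The document supplied as the SAP is a results report. Table 4 (section 7.1), Table 5 (section 7.2) and the repeatability table (section 8) are split by febrile status. Section 7.3 gives one pair of limits, +0.86 and −0.80, with a plot titled for n=110. Section 7.4 gives one R² of 0.80 for all subjects, "indicating a strong linear relationship".

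The Discussion states: "The limits of agreement did not exceed 0.86 (absolute value) and clinical bias did not exceed 0.03°F for the study population overall". It presents these two figures as strong signs of agreement and as superior to the comparator study. It then discloses the group result: "The highest bias attained was 0.25°F for subjects in the welloStationX febrile subject group". On correlation it says: "The correlation coefficient of 0.80 supports this strong linear relationship".

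**The concern.** Protocol 2.0 and 3.1 place the device in fever screening, so a reader needs to know how it agrees with the oral thermometer in febrile and in afebrile subjects separately. The protocol planned for that. The report split the bias but not the limits of agreement or R², and its headline accuracy statement rests on pooled values.

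If the bias differs between groups, a pooled mean depends on how many febrile subjects were enrolled as well as on the device. A small pooled bias can then come from two group biases of opposite sign. The figure of 0.03°F is nonetheless set against the comparator's overall 0.20°F as evidence of superiority. No confidence interval accompanies any bias or limit, although Protocol 1.1 asks for the bias with its uncertainty.

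**Working it through.** **Inputs.** Section 4 of the report: 33 febrile, 77 afebrile. Table 5 (section 7.2), bias ± SD in °F: febrile 0.25 ± 0.33, afebrile −0.06 ± 0.42, all 0.03 ± 0.42. Table 4, mean (SD): febrile device 99.83 (0.60), reference 99.58 (0.71); afebrile device 98.15 (0.47), reference 98.22 (0.29).

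**1. Reproduce the pooled figures from the groups.**
- Bias: (33 × 0.25 − 77 × 0.06)/110 = 3.63/110 = 0.033.
- SD: √[(32 × 0.33² + 76 × 0.42² + (33 × 77/110) × 0.31²)/109] = 0.419.
- Limits: 0.033 ± 1.96 × 0.419 = −0.79 to +0.85. Rounding of the inputs allows −0.80 to −0.77 and +0.84 to +0.87.

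The reported pair is therefore the result for all 110 subjects.

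**2. Group results.** The limits are bias ± 1.96 × SD. The SE of a limit is SD × √[1/n + 1.96²/(2(n−1))], which is 0.099 febrile and 0.082 afebrile. Intervals use the t distribution.

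| | Bias (95% CI) | Limits | Width | Largest absolute limit (95% CI) |
|---|---|---|---|---|
| Febrile | 0.25 (0.13 to 0.37) | −0.40, +0.90 | 1.29 | +0.90 (0.69 to 1.10) |
| Afebrile | −0.06 (−0.16 to 0.04) | −0.88, +0.76 | 1.65 | −0.88 (−1.05 to −0.72) |
| All, as reported | 0.03 | −0.80, +0.86 | 1.66 | +0.86 |

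The group limits are shifted relative to the pooled ones, not wider.

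**3. Difference between groups.** 0.25 − (−0.06) = 0.31; SE = √(0.33²/33 + 0.42²/77) = 0.075; Welch t = 4.15 on 76 df; 95% CI 0.16 to 0.46.

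**4. Dependence on case mix.** With febrile share p, the pooled bias is 0.25p − 0.06(1 − p). It is 0.033 at 30%, 0.064 at 40% and 0.095 at 50%. Protocol 3.2.1 allows 30% to 50%.

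**5. Correlation.** r = (SD_device² + SD_ref² − SD_diff²)/(2 × SD_device × SD_ref).
- Febrile: (0.3600 + 0.5041 − 0.1089)/0.852 = 0.89.
- Afebrile: (0.2209 + 0.0841 − 0.1764)/0.2726 = 0.47.
- Overall, with total SDs of 0.926 and 0.774 rebuilt from Table 4 as in step 1: r = 0.89, R² = 0.80.

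So 0.80 is R², as section 7.4 labels it, and not the correlation coefficient. The low afebrile value is partly due to a narrow reference range (SD 0.29).

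**6. Febrile classification.** Section 4 states: "33 subjects (30%) were febrile, with fever defined as a core temperature of 99.5°F (37.5°C) or higher". Suppose all 33 oral readings were at least 99.5 with a mean of 99.58. The SD is then largest when one reading holds all the excess: (99.58 − 99.5) × √33 = 0.46, or 0.49 if the mean is 99.585 before rounding. Table 4 gives 0.71. Some subjects classed as febrile must therefore have had oral readings below 99.5, or one of these figures is wrong.

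**7. Direction of the difference.** Section 7.2 describes reference minus device. Table 4 gives 99.83 − 99.58 = +0.25, which is device minus reference.

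**The case against.** Little information is hidden. Table 5 gives group bias and SD, from which anyone can derive the limits, and the Discussion states the febrile bias and compares it with the comparator's largest group bias (0.25 against 0.32). The quoted sentence is true as written, because it refers to the overall population. The largest limits move only from 0.86 to 0.88 and 0.90, within sampling error, and stay below the comparator's 1.21. Case mix overturns nothing: the pooled bias would reach the comparator's 0.20 only at (0.20 + 0.06)/0.31 = 84% febrile, and the range 0.03 to 0.10 lies inside the pooled 95% CI of about −0.05 to 0.11. Protocol 4.1 names only accuracy and repeatability as primary measures, and 4.2 asks for bias ± SD, which was given.

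The group figures also rest on a classification that does not fit the reported data. If device readings played any part in it (an assumption; the documents do not say), that alone would push the bias up in febrile and down in afebrile subjects, which is the pattern seen.

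Much of this stands and limits the weight of the point. It does not supply the missing results. Limits of agreement are a primary endpoint in the synopsis and part of the 4.2 primary analysis. The qualifier in 4.2 does not excuse the omission, since the group limits follow from numbers already tabulated. The classification argument is a reason to settle that question first. The figures were not available, so nothing is claimed about what the plots show.

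**Conclusion.** The concern holds. The report text omits limits of agreement and correlation by febrile status, and its headline bias of 0.03°F is a 30/70 average of two biases that differ by 0.31°F. The febrile bias of +0.25°F has an interval that excludes zero. The statement that the limits do not exceed 0.86 applies to the pooled sample only; the group values are 0.90 and 0.88, a difference of 0.02 to 0.04°F. The label on 0.80 in the Discussion is wrong, and correlation is not evidence of agreement. The direction of the bias in section 7.2 contradicts Tables 4 and 5.

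The documents set no numerical acceptance limit, so none of this shows that the device fails, and the comparison with the comparator study is not reversed. The group limits and correlations here come from rounded summaries and assume that the febrile grouping is sound. The omission itself is certain; the size of the group difference is provisional until the grouping is explained.

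**What to change.** 1. State which reading assigned each subject to the febrile or afebrile group, and reconcile this with the febrile reference mean and SD in Table 4.
2. From subject-level data, report bias and limits of agreement with 95% confidence intervals, and r, for febrile, afebrile and all subjects. Base the accuracy statement on the group results as well as the pooled ones.
3. State the direction of the difference once and make section 7.2 agree with Tables 4 and 5.
4. Correct the label (R² = 0.80, r about 0.89) and stop citing correlation as support for agreement.

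The cost is a few lines of analysis on data already held, plus the classification check. The largest absolute limit becomes slightly less favourable (0.90 against 0.86), while the febrile interval is narrower than the pooled one (1.29 against 1.66). Group values may change after step 1.

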7.1 Means and Standard Deviations

Table 4 below shows the mean and standard deviation of temperature readings in °F with the welloStationX (DUT) and the Welch Allyn SureTemp (reference thermometer) by febrile versus afebrile subject groups.

Table 4: Means and Standard Deviations by Febrile Status

Temperature Reading (°F)	welloStationX Febrile (n=33)	Welch Allyn Febrile (n=33)	welloStationX Afebrile (n=77)	Welch Allyn Afebrile (n=77)
Mean	99.83	99.58	98.15	98.22
Standard deviation	0.60	0.71	0.47	0.29

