7.2 Clinical Bias

Agreement through clinical bias evaluation was calculated as the Mean Bias \pm SD by subtracting the first output measurement recorded with the welloStationX thermometer (DUT) from the corresponding output measurement recorded with the Welch Allyn SureTemp oral thermometer for each subject, and then calculating the Mean Bias \pm SD of the biases.

Table 5 below shows clinical bias by febrile status.

Table 5: Clinical bias by febrile status.

Mean bias \pm SD Febrile (n=33)	Mean bias \pm SD Afebrile (n=77)	Mean bias \pm SD All (n=110)
0.25 °F \pm 0.33	-0.06 °F \pm 0.42	0.03 °F \pm 0.42

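### Bias differs by febrile status (+0.25°F febrile, -0.06°F afebrile), so the pooled 0.03°F does not describe agreement in febrile subjects, and the limits of agreement planned by febrile status are not reported

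*SAP*

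**What the plan says.** Protocol 4.2 plans the mean bias with its SD, limits of agreement and a "Band-Altman plot created using mean bias and standard deviation data". It then commits to showing all analyses separately for febrile and afebrile subjects. Protocol 3.2.1 allows a febrile share of 30% to 50%. Protocol 4.3 judges success by close agreement with the reference and by agreement values no worse than those published for the Caregiver.

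In the results report:

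- Section 4: "Subjects were 110 males and females aged 5 years of age and older: 33 subjects (30%) were febrile"; the other 77 were afebrile.
- Section 7.2, Table 5: bias ± SD is 0.25 ± 0.33 (febrile), -0.06 ± 0.42 (afebrile) and 0.03 ± 0.42 (all), in °F.
- Section 7.3: limits of agreement are given once, pooled, as +0.86 and -0.80.
- Discussion: "The limits of agreement did not exceed 0.86 (absolute value) and clinical bias did not exceed 0.03°F for the study population overall". It ranks these values above the Caregiver's overall bias of 0.20°F and largest limit of 1.21. It also states the 0.25°F febrile bias and sets it against 0.32°F in the Caregiver's afebrile group.
- Section 7.2 defines the bias as "subtracting the first output measurement recorded with the welloStationX thermometer (DUT) from the corresponding output measurement recorded with the Welch Allyn SureTemp oral thermometer", that is, reference minus device.
- Section 7.1, Table 4, in the column order device febrile, reference febrile, device afebrile, reference afebrile: "Mean 99.83 99.58 98.15 98.22" and "Standard deviation 0.60 0.71 0.47 0.29".

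**The concern.** A single mean bias and one pair of limits summarise agreement well only if the bias is roughly the same across the subjects pooled. Here the two groups lean in opposite directions, so the pooled mean depends on how many febrile subjects were enrolled as well as on the device. The device is being evaluated for fever screening, and agreement in febrile subjects is the part of the evidence that matters most for that use. A reader who takes 0.03°F from the Discussion would understate the febrile bias roughly eightfold (0.25/0.03 = 8.3). Ranking one study's pooled bias against another's is also not like for like unless the febrile shares match.

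**Working it through.** **Inputs.** Section 4 (33 and 77 subjects), Table 4 (means and SDs), Table 5 of section 7.2 (bias and SD of the differences).

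**1. Reproduce the report's pooled figures.**
- Bias = (33 × 0.25 - 77 × 0.06)/110 = 0.033. Reported: 0.03.
- Variance of differences = [32 × 0.33² + 76 × 0.42² + (33 × 77/110) × 0.31²]/109 = (3.485 + 13.406 + 2.220)/109 = 0.175, so SD = 0.419. Reported: 0.42.
- Limits = 0.033 ± 1.96 × 0.419 = -0.79 to +0.85. Reported: -0.80 and +0.86, within rounding.
- Overall variances rebuilt from Table 4 are 0.858 (device column) and 0.599 (reference column). With the SD above they give R² = 0.80, as reported.

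**2. Bias by group.**
- Febrile: 0.25 ± 2.037 × 0.33/√33 = 0.13 to 0.37, which excludes 0.03.
- Afebrile: -0.06 ± 1.992 × 0.42/√77 = -0.16 to 0.04.
- Difference: 0.25 - (-0.06) = 0.31; SE = √(0.33²/33 + 0.42²/77) = 0.075; 95% CI about 0.16 to 0.46; 0.31/0.075 = 4.1.

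**3. Dependence on the mix.** With febrile share p and the group biases unchanged, pooled bias = 0.25p - 0.06(1 - p). This is 0.033 at p = 0.30 and 0.125 - 0.030 = 0.095 at p = 0.50.

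**4. Limits by group.**
- Febrile: 0.25 ± 1.96 × 0.33 = -0.40 to +0.90 (width 1.29).
- Afebrile: -0.06 ± 1.96 × 0.42 = -0.88 to +0.76.
- Pooled as reported: -0.80 to +0.86 (width 1.66).

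Each group's outer limit is slightly beyond 0.86, by 0.04 and 0.02. That is small against sampling error. The SE of a limit is about SD × √(1/n + 1.96²/(2(n - 1))), which is 0.10 febrile and 0.08 afebrile.

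**5. Trend with temperature.** Slope of difference (device minus reference, as Table 4 is labelled) on the average of the two readings = [(s_D² - s_R²)/2] / [(s_D² + s_R²)/2 - s_diff²/4].
- All subjects: 0.19°F per °F (t = 4.2).
- Afebrile: 0.0684/(0.1525 - 0.0441) = +0.63 (p < 0.0001).
- Febrile: -0.0721/(0.4321 - 0.0272) = -0.18 (p = 0.05).
- All subjects, on the reference reading alone: 0.07 (p = 0.18).

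**6. Total error.** √(bias² + SD²) = 0.41 febrile and 0.42 afebrile.

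**7. Sign and Table 4.**
- Device minus reference in Table 4 gives 99.83 - 99.58 = +0.25 and 98.15 - 98.22 = -0.07, matching Table 5 within rounding. The wording of section 7.2 would give the opposite signs.
- If all 33 febrile oral readings were at least 99.5, a mean of 99.58 leaves a total excess of 33 × 0.08 = 2.64. The SD is largest when one subject carries all of it: √[(2.64² - 33 × 0.08²)/32] = 0.46, or 0.49 allowing for rounding of the mean. Table 4 prints 0.71.

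**The case against.** The report does not hide the febrile bias: it is in Table 5 and in the Discussion, with a comparison to the Caregiver's worst group. Nor would the pooled ranking on bias reverse, since 0.095 at 50% febrile is still below the Caregiver's 0.20. Protocol 4.2 is sound here because it asks for analyses by febrile status; the gap lies in the report. The Discussion's sentence is also expressly about the population overall, and of that it is true. The febrile limits reach only 0.04 beyond the pooled upper limit, and the febrile interval is narrower. All of this stands. It limits the weight of the point but does not make 0.03°F a measure of agreement in fever.

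A reader might infer from the overall slope of 0.19 that disagreement grows with temperature, and project larger errors at 100 or 101°F. The documents do not support that. The slope comes largely from the gap between two clusters; within groups it has opposite signs, and on the reference alone it is not distinguishable from zero. Scatter is smaller in febrile subjects (0.33 against 0.42) and total error is about equal. No single line describes these data, and the Bland-Altman figure is not available to settle the shape.

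A further caution concerns the sign. Either the Table 4 columns are interchanged or febrile status was not set by the oral reading. Grouping subjects on one of the two readings being compared can itself create part of a gap in bias, so the 0.31°F need not be entirely a property of the device.

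**Conclusion.** The point holds as a reporting and interpretation fault that should be fixed. Bias differs between the groups by 0.31°F (95% CI about 0.16 to 0.46). The pooled 0.03°F averages opposite-signed values at one enrolment mix and should not serve as an indicator of close agreement or of superiority to the Caregiver. Limits by febrile status were planned and are missing. When derived, they change the outer bound only slightly, but they show that errors lean in opposite directions in the two groups.

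This rests on rounded summary tables, on 1.96 SD limits within each group, and on Table 5 being correct apart from its sign. Interchanging the Table 4 columns would leave the size of the gap unchanged but would decide whether the device reads high or low in fever. The documents do not say which. They also give no Caregiver limits by group, so a like-for-like febrile comparison of limits cannot be made from them.

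**What to change.** 1. Reconcile first: state whether bias is device minus reference or the reverse, make section 7.2 and Tables 4 and 5 agree, say which reading set febrile status, and check the febrile Welch Allyn mean and SD against the 99.5°F definition.
2. In section 7.3, give the bias with its 95% CI and the limits of agreement for febrile and afebrile subjects separately, as Protocol 4.2 already requires.
3. In the Discussion, remove the 0.03°F clause as an indicator of close agreement. Base the agreement statement and the Caregiver comparison on values for the matching febrile groups, and state where the Caregiver source gives none.
4. Plot and regress the differences against temperature, with a check of linearity. Do not impose one line across both groups or quote extrapolated figures at 100 to 101°F.

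The cost is a short reanalysis of data already collected and revised wording. The downside for the sponsor is a less favourable headline bias.

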4.0 STATISTICAL ANALYSIS PLAN

4.1 Primary Outcome Measures

The Primary Outcome Measures for this study are to evaluate:

1. Clinical Accuracy of the welloStationX; and
2. Clinical Repeatability of the welloStationX

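### The reported overall repeatability (0.06, or 0.062) is below both group values (0.13 and 0.09), which a pooled SD cannot be; pooling those group values gives about 0.10

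*SAP*

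**What the plan says.** Protocol Section 4.1 lists "Clinical Repeatability of the welloStationX" as the second of two primary outcome measures. Protocol Section 4.2 fixes the method: "Repeatability will be calculated using the pooled standard deviations formula". Section 8 of the results report says this was done: "Clinical Repeatability was calculated using the pooled standard deviations of the triplicate measurements recorded by the welloStationX".

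The repeatability table in Section 8 (the second of two tables numbered 5) gives febrile 0.13 (n=33), afebrile 0.09 (n=77) and all subjects 0.06 (n=110). The Discussion confirms the group values, "at 0.13 and 0.09, respectively", and gives the overall figure to one more digit: "The notably low clinical repeatability of 0.062 for subjects overall". It then sets these values against the comparator thermometer's 0.21 febrile, 0.15 afebrile and 0.17 overall.

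Report Section 4 shows that the two groups make up the whole sample: "33 subjects (30%) were febrile" and "77 subjects were afebrile", of 110. Neither document gives a different formula or a different subset for the overall figure.

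**The concern.** The overall figure is smaller than both of the figures it should combine. Pooling averages variances, and an average cannot fall outside the range of its parts. The comparator's three values, quoted in the same part of the Discussion, behave as they should: 0.17 lies between 0.15 and 0.21.

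The overall value opens the report's repeatability argument, is compared with 0.17, and supports the Conclusion's statement on precision. The report was written to answer a regulator's request for clinical accuracy testing. A primary-outcome table whose three entries cannot all be true undermines that purpose, and a reader can see the conflict without the data.

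**Working it through.** **Inputs**
- Febrile: n = 33, SD 0.13. Afebrile: n = 77, SD 0.09 (report Sections 4 and 8, and Discussion).
- Overall: 0.06 (Section 8) or 0.062 (Discussion).
- Three readings per subject ("Each subject's temperature was measured three separate times sequentially using the study device", report Section 5), so 2 within-subject degrees of freedom each.
- Unit: the report prints none for repeatability. °F is assumed, as in its Table 4.

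**1. Trying to reproduce 0.062**

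Pooled SD = sqrt[(33×2×0.13² + 77×2×0.09²)/(110×2)]. The factor 2 cancels:

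sqrt[(33×0.0169 + 77×0.0081)/110] = sqrt[(0.5577 + 0.6237)/110] = sqrt(0.01074) = **0.104**

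At the rounding limits of the inputs, 0.125 with 0.085 gives 0.099, and 0.135 with 0.095 gives 0.109. The reported value is not reproduced.

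**2. Other ways of combining the two groups**

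| Method | Result |
|---|---|
| Pooled, weights n−1 | 0.1035 |
| Pooled, weights 3n−1 | 0.1036 |
| Pooled, equal weights | 0.112 |
| n-weighted mean of the SDs | 0.102 |
| n-weighted geometric mean | 0.1005 |
| n-weighted harmonic mean | 0.099 |

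Every average lies between 0.09 and 0.13.

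**3. Whether one wrong group value could explain 0.062**

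- Suppose the febrile value is right and every afebrile subject had zero variation. With the lowest SD that rounds to 0.13, overall = sqrt(33×0.125²/110) = 0.068, already above 0.062.
- Suppose the afebrile value is right and every febrile subject had zero variation. With the lowest SD that rounds to 0.09, overall = sqrt(77×0.085²/110) = 0.071, again above 0.062.
- With overall 0.062 and febrile 0.13, the afebrile variance would be (110×0.062² − 33×0.13²)/77 = −0.00175, which is impossible.
- For 0.062 to hold, the febrile SD could be at most 0.062/sqrt(33/110) = 0.113, and the afebrile SD at most 0.062/sqrt(77/110) = 0.074. Both group values would have to be wrong.

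**4. Operations other than pooling**

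- Pooled SD/√3 = 0.060 (0.057 to 0.063 with rounding). This is the standard error of a three-reading mean, not the repeatability that the documents define. It is a possible cause, not an established one.
- Conversion to °C: 0.1036/1.8 = 0.058 (0.055 to 0.060 with rounding), which does not reach 0.062.

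**5. Size, if the group values stand**

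- Understatement: 1 − 0.062/0.1036 = 40%.
- Margin below the comparator's 0.17: 1 − 0.062/0.17 = 64% as reported; 1 − 0.1036/0.17 = 39% after correction.
- As an illustration, the 95% limit for the difference between two repeat readings, 2.77 × SD, is 2.77×0.062 = 0.17°F as reported and 2.77×0.1036 = 0.29°F after correction.

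**The case against.** The strongest objection is that the documents do not show which figure is wrong, so 0.10, the 40% understatement and the 39% margin all depend on the group values being right. That stands, and it is why all three values need recomputing. Step 3 does favour an error in the overall figure, because otherwise both group values must be wrong.

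The consequence is also limited. Protocol Section 4.3 sets no numerical threshold for repeatability; it asks for agreement values comparable to or better than the comparator's. A value of 0.10 is still below 0.17, and the group comparisons (0.13 against 0.21, 0.09 against 0.15) do not use the overall figure. So no stated decision reverses. The figure is nonetheless a primary-outcome result, and it is impossible as printed.

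Three smaller points are fair. The unit is an assumption. The 2.77 multiplier is used in neither document and applies one normal-theory SD to groups that differ. The Discussion's remark about absolute differences between repeats can be read as an inference from a small SD rather than as a definition, so that criticism concerns clarity only.

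Finally, the planned method in Protocol Section 4.2 is sound. The fault is in the reported result.

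**Conclusion.** The concern holds. Febrile 0.13, afebrile 0.09 and overall 0.06 (0.062) cannot all be pooled within-subject SDs for the same 110 subjects on one scale, whatever the weighting, and rounding does not explain the gap. Assuming that the two group values are correct and in °F, the overall repeatability is about 0.10°F (0.099 to 0.109). The printed value then understates the SD by about 40%, and the advantage over the comparator is about 39% rather than about 64%. The result becomes less favourable but stays below the comparator. The cause of the error cannot be settled from the documents.

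**What to change.** - Recompute the febrile, afebrile and overall values from the subject-level triplicates with one formula: the square root of the sum of subject variances divided by the number of subjects. If any subject has fewer than three readings, weight each variance by its degrees of freedom.
- Check that the overall value lies between the two group values, and record what caused the discrepancy.
- Replace 0.06 in the Section 8 table and 0.062 in the Discussion with the result (about 0.10 if the group values stand), and state the unit.
- Restate the comparison with 0.17 and reconsider the strength of the wording on precision.
- Describe the quantity as a within-subject SD. If the size of repeat-reading differences is to be discussed, derive it explicitly from that SD.

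The cost is one recalculation on existing data and a correction to a table and a few sentences.
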